4.1. SUBJECT POPULATION

Fifty-two subjects will be enrolled in the study. We anticipate that 150 potential subjects will be approached in order to reach this goal (i.e., 1 in 3 potential subjects will be eligible and choose to enroll). If subjects drop out after enrollment, they will not be replaced.

Vulnerable populations, including children, pregnant women, those who are unable to perform consent, and prisoners will not be eligible for this study.

4.2. STUDY INTERVENTION

TENS is listed as non-significant risk when used for chronic pain in the 2006 FDA's "Significant Risk and Non-significant Risk Medical Devices" Guidance. 20 The study device has been cleared by the FDA under K152954. It is an over-the-counter device that is approved for chronic pain. Although it will be used for a different indication in this study (i.e., peripheral edema), the TENS device will be used on the same location of the body and in the same manner as it is suggested for use in the user's manual. The device does not require a prescription and is widely available. Furthermore, TENS has been studied in patients with peripheral edema in two previous studies.^{9, 10} Therefore, we believe that it poses nonsignificant risk in this study and does not require and IDE. It emits a 60-100 Hz stimulation. The device is worn on the upper calf right below the knee and secured by an elastic band. The device is controlled by an application and alternates between a 1-hour treatment period and 1-hour rest period on the automated setting. Subjects will be asked to use the device for 7 to 8 hours per day on the automated setting. They will be asked to alternate the leg they wear the device on each day in order to minimize potential skin reactions. Subjects will be allowed to use the device while sleeping (overnight use of this device is approved by the FDA for chronic pain). If they choose to do so, they will not be asked to wake early to remove the device after 8 hours and thus could receive slightly longer stimulation. How often subjects choose to use the device while sleeping will be used to inform a future study.

Device setting. The device emits electrical stimulation for the entire 1-hour treatment period, resulting in 4 hours of total stimulation in 7 to 8 hours of use.

The 7 to 8 hours of use (4 hours of stimulation) was chosen based on the experience of the 3 individuals who reported the positive effects on peripheral edema (see Preliminary data) and assuming more stimulation is better.

The devices will be stored in a locked storage room in the Translational Pain Research Program offices at [name]. All study devices will be returned to the study staff after the 3-week treatment period. The devices will then be sent back to the device manufacturer (Neurometrix Inc., Woburn, MA).

Page 7 of 26

5. INCLUSION AND EXCLUSION CRITERIA

Inclusion criteria (subjects must...)

- 1. Have had lower extremity edema for at least 3 months.
- 2. Currently have edema of at least 2+ (i.e., 3-4mm depression rebounds within a few seconds, but not immediately) on the pitting scale. ²¹ Pitting will have been assessed by a Clinician, the clinician Co-I within 6 weeks of the screening visit or at the screening visit by the research staff.
- 3. Willing to not start or change the dosages of any medications that could affect edema for 2 weeks prior to enrollment, and throughout the duration of the study.
- 4. Not currently using diuretics to control their edema.
- 5. Not currently using and willing to not start using occupational therapy, physical therapy, or lymphatic massage for edema (at home or by PT) 2 weeks prior to and throughout the duration of the study.
- 6. Not currently using compression stockings or Velcro or bandage wraps at least 2 weeks prior to enrollment in the study or based on shared decision making of the potential subjects' clinician or the clinician co-investigator are receiving sufficiently little benefit from these therapies to warrant stopping their use for the duration of the study.
- 7. Have access to a smart phone or device with an Apple or Android operating system with iOS 10 or later, or Android 6 or later. iOS and Android devices must have Bluetooth Low Energy (LE, also called Bluetooth Smart) compatibility. The smart phone or device must have the ability to access the TENS device's Quell App and, the ability to connect to the cellular data or Wi-Fi on a daily basis during the trial.
- 8. Have an active and accessible email.
- 9. Be willing and able to regularly check the email provided throughout the study.
- 10. Be able to read English (i.e., is literate, can speak English, and is not blind) because patient-reported outcomes and consent form are only available in English.
- 11. Be at least 18 years of age.
- 12. Be able to provide informed consent.

Exclusion criteria (subjects must not...)

- 1. Be currently using a TENS device for any reason.
- 2. Have an acute and symptomatic lower extremity DVT (i.e., the diagnosis of DVT is less than 3 months prior to study enrollment).
- 3. Have had a stroke in the past 3 months
- 4. Have lower extremity wounds or ulcers.
- 5. Have a cardiac pace maker or defibrillator.
- 6. Have epilepsy.
- 7. Have a leg that is too small or too large for the TENS device to fit securely.
- 8. Have cellulitis or fibrosis.
- 9. Have any skin condition at the site where the electrode pads adhere such that the PI/CoI think the device will not be safe for the subject.
- 10. Have congestive heart failure.

Page 8 of 26

- 11. Have chronic kidney disease of stage 3 or greater.
- 12. Have cirrhosis of the liver.
- 13. Have previous surgery that removed lymphatic lower leg tissue.
- 14. Have a diagnosis of lower limb lymphedema.
- 15. Be pregnant or planning to become pregnant within the next 8 weeks.

6. RECRUITMENT METHODS

Subjects will be recruited from the URMC hematology providers, including [name] (CoPI) and his colleagues. In order to facilitate identification of potential subjects, the study coordinator will screen patient records of clinicians who have granted permission. The coordinator will alert the clinician to potentially eligible patients and the clinician will introduce the patient to the coordinator if they are interested in hearing about the study. [name], an occupational therapist in the URMC Occupational Therapy Department has agreed to refer patients to the study. Flyers and study brochures will be used to advertise the study in waiting rooms of the hematology clinic, occupational therapy clinic, and the willing members of primary care offices that are associated with the URMC. The CTSI's Research Match program will be used to identify potentially eligible patients who are willing to be contacted directly for research.

7. CONSENT PROCESS

Prior to performing any consent-related activities the potential subjects' identification will be verified using information already known by both parties (e.g., DOB, middle name, street name). The consent process will be performed at the Pre-baseline visit by a coordinator. The potential subject will be informed that their medical care will not be changed in any way if they decide not to participate. The coordinator will review the consent form with the potential subject and allow time for questions. The potential subject will be allowed to take home the consent form and discuss it with family or friends before proceeding with consent if they so choose. After the consent form has been reviewed, the potential subject will be asked the following series of questions, by the consenter, to assess how well they understand the study: (1) If you join the study can you wear compression stockings? (2) How many in-person visits are we asking you to complete? (3) What is the longest time that you will be asked to participate in the study? If the potential subject answers any of the questions incorrectly, the information will be re-explained to them and they will be asked the question they missed a second time. The subject and the PI, Co-I, or designated study staff member will sign the consent form. A copy of the form will be given to the subject and the original will be kept in the study records in a locked cabinet and a copy will be sent to HIM to add the study to the medical record.

8. STUDY PROCEDURES

Screening Procedures

Patients of collaborating clinicians

Page 9 of 26

Patient records of collaborating clinicians will be screened for initial eligibility. All eligibility criteria that can be found in the medical charts (e.g., use of diuretics for peripheral edema) will be reviewed prior to approaching potential subjects. Potentially eligible subjects will be invited by the clinician (in-person or via MyChart, phone call, or signed letter) to complete the screening process. The coordinator will ask the screening questions via phone (or in person if the subject is at the clinic for a visit with their clinician). If the potential subject has not had the severity of their edema evaluated by the clinician within 6 weeks of the Pre-baseline visit, the severity of their pitting of edema will be evaluated at the Pre-baseline visit by the trained study staff to confirm final eligibility prior to obtaining informed consent.

Individuals who call in response to flyers

Potential subjects who contact the coordinator in response to flyers or brochures placed in clinical offices will be asked all of the screening questions that they can answer on the phone. If they are potentially eligible, they will be asked if the coordinator can access their medical chart to confirm entry criteria, diagnosis of edema, medications. If the entry criteria are met, they will be invited to come in for the Pre-baseline visit, at which point the severity of their pitting of edema will be evaluated by the trained study staff to confirm final eligibility prior to obtaining informed consent.

If potential subjects are not eligible or choose not to participate, their linked health and identifying information will be destroyed. De-identified reasons for ineligibility or a choice not to participate will be documented in a screening log. De-identified data related to reasons for ineligibility or choice not to participate will be used to improve the entry criteria of a future study in order to potentially increase feasibility and generalizability.

Individuals who are identified via Facebook and Research Match

People who contact study personnel using the study Facebook ad or Research Match platform will click on a survey link, which will take them to a REDCap initial eligibility screening survey. In this eligibility screening survey, we will utilize REDCap branching logic so that as soon as a potential subject enters a response that renders them ineligible for the study, when they click 'Next', they will be prompted with the following message:

"Thank you for your time. Unfortunately, you are not eligible for this study."

The de-identified data from ineligible subjects will be kept, but they will only be asked questions in the eligibility survey up until one of the questions makes them ineligible. We are keeping this data only to find out the reasons that make people ineligible. This data will help find out, what questions are confusing to people and if there is anything that can be modified to make the protocol and workflow better.

Potential subjects who meet all of the eligibility criteria contained in the survey will be prompted with the following message on the final page:

Page 10 of 26

"Thank you! You might be eligible for this study. If you are interested in learning more about our study, please provide your contact information below so that our study team can contact you."

The UR Health Research Facebook page: https://www.facebook.com/URHealthResearch, which is managed by CTSI will be hosting these recruitment materials.

Medical record documentation of study participation

After a subject provides informed consent, a copy of the signed consent form will be uploaded into eRecord. A note in eRecord will indicate that the subject has signed consent for a clinical study. The note will include the study title, that the subject will be using a TENS device for peripheral edema during the study, and the PI's contact information for questions regarding the study.

Study visit schedule

See Tables 2 and 3 for the schedule of assessments and procedures. The total duration of the study will be up to 8 weeks (1 Pre-baseline week, 1 Treatment period of 3 weeks, and one follow-up phone call 4 weeks after the Treatment period). In order to control for time-of-day factors that contribute for edema, the study visits for an individual subject should ideally all occur within a +/-2-hour time window whenever possible; although this is not required. For example, if a subject's first study visit is at 3pm, Visit 2 should occur between 1pm and 5pm.

To ensure appropriate safety precautions related to COVID-19 when conducting in-person study procedures, the process for conducting in-person visits outlined in the Guidance for Human Subjects Research will be followed.

(https://www.urmc.rochester.edu/coronavirus/coronavirus-research/guidanceforresearchers/human-subjects-research.aspx). A RSRB approved flyer is available to help subjects understand what they can expect when a study visit occurs.

Table 2: Schedule of events

| Events | Pre- Baseline visit (Visit 1) | Baseline period (1 week) | Baseline visit (Visit 2) | Treatment period (3 weeks) | Treatment endpoint (Visit 3) |
|--|--|--------------------------------|--------------------------------|----------------------------|------------------------------------|
| Final eligibility check* | X | | | | |
| Consent | X | | | | |
| Instruct subjects how to use Fitbit device | X | | | | |

Page 11 of 26

| Instruct subjects how to complete at-home paper PROs | X | | | | |
|---|---|---|------------|---|---|
| Use Fitbit daily | | X | | X | |
| Complete daily or weekly at-home paper PROs | X | X | | X | |
| Distribute of study TENS device and teach subject how to use it | | | X | | |
| Complete visit electronic PROs | | | X | | X |
| Functional exam measures | | | X | | X |
| Leg measurements | X | | X | | X |
| COVID Screening form | X | | X | | X |
| Open subject's Quell App and Fitbit while connected to Wi-Fi | | | X 1 | | X |
| Adverse event monitoring ² | | | | X | X |
| Qualitative interview | | | | | X |

^{*}If edema has not been assessed by a clinician within 6 weeks of Pre-baseline visit.

SCREENING / CONSENT

Reminder 1: (phone call) (1-2 days prior to Visit 1). Remind the potential subject (and record in the **Telephone Contact Form**):

- To complete the COVID-19 pre-screen questionnaire prior to the visit.
- Of the date, time of their Visit 1.

Visit 1: Pre-baseline (In-person / Day -7)

If the potential subject has not had the severity of their edema evaluated by the clinician within 6 weeks of the Pre-baseline visit, the severity of their pitting of edema will be evaluated at the Pre-baseline visit by the trained study staff to confirm final eligibility prior to obtaining informed consent.

The coordinator will perform the informed consent process as per description above. The coordinator will confirm whether the subject has received a copy of the URMC and Affiliates

Page 12 of 26

¹ Pair only the Fitbit device

² Additional phone call after 1 week of TENS use

Notice of Privacy Practices; if not, the subject will receive a copy of the URMC and Affiliates Notice of Privacy Practices.

The coordinator will confirm the following with the subject: whether the subject has active email for preferred method of contact, active Phone # for preferred method of contact, whether or not it is acceptable to leave messages about the study at the provided phone number

The coordinator will perform leg measurements and document them. The coordinator will help the subject setup the Fitbit device, review the user guide and discuss how to use the Fitbit. They will ask the subjects to use the Fitbit at all times (unless they cannot tolerate it while sleeping) until Visit 2.

The coordinator will help the subject register or create an account for direct payments through Advarra Participant Payments, if they do not already have one. The coordinator will provide the subject with the Information Sheet for Advarra Participant Payments. The coordinator will review the two visits that study payments will be initiated through the direct payment system.

The subject will report any medications that could affect their edema. In addition, a coordinator will check the medical record for medications that may cause swelling. The subject will be asked to write in these medications on the medication diary in which the subjects will be asked to document use of medications that could affect edema.

The coordinator will explain how to complete the at-home (paper) PROs.

PRE-BASELINE ASSESSMENT PERIOD

Week -1: (subject will complete at home)

- Subject will use the Fitbit device at all times while awake.
- Subject will setup their Advarra account and choose payment type payments
- Subject will complete the Edema Symptom Pre-Baseline Daily Diary.
- The coordinator will setup times and dates for the **Baseline visit**, **Treatment period Endpoint** visit and follow-up phone call.

.

Reminder 2: (phone call or email) (1 day prior to Visit 1)

Remind the subject (and record in the **Telephone Contact** form):

- Of the date, time, and location of their next in-person study visit.
- To complete the COVID-19 pre-screen questionnaire prior to the visit.
- To complete the visit PROs online via REDCap prior to the visit.
- To bring their completed at-home (paper) PROs from Week -1.
- To bring their Fitbit and mobile device.
- To wear pants with a loose leg.

Page 13 of 26

TREATMENT PERIOD

Visit 2- Baseline visit: (In-person / Day 0 up to + 5_days)

The coordinator will download the Quell App to the subject's mobile device, setup a Quell Health account for the subject (using valid de-identified study email address and password) and help them pair the TENS device to their mobile device and calibrate it. They will introduce the concept of TENS and describe how it is likely to feel to the subjects using a standardized script. They will give the subject 2 electrode strips along with the TENS device, which should be sufficient for the 3-week duration of the treatment period of the study. They will provide the subject with the subject guide to help them with at-home use and ask them to use the device between 7 to 8 hours per day. They will also ask them to open the Quell App once a day while the device is connected to cellular data or Wi-Fi to transfer the data to the Quell Health account. If the subject plans to use cellular data, the coordinator will setup the Quell App to allow the use of cellular data in the settings.

The coordinator will review the Edema Symptom Daily Diary, Edema Symptom Inventory Week Recall, and Edema Symptom Inventory-Week Recall 0-10 Scale forms and teach the subject how to complete them.

The coordinator will perform the ankle range of motion and lower limb sensation tests and measure the subject's lower limbs using the volumeter and tape measure.

The subject will complete the visit related patient-reported outcome measures (PROs) at the study visit if they were not completed previously using the REDCap link.

Weeks 1-3: (subject will do at home)

- Subject will use the Fitbit Device at all times.
- Subject will use the TENS device for 7 to 8 hours / day either day, night, or asleep.
- Subject will complete the Edema Symptom Daily Diary, Edema Symptom Inventory Week Recall, and Edema Symptom Inventory-Week Recall 0-10 Scale.

Phone Call 1: (Day 7, up to +2 days)

- AE assessment: The coordinator will ask the subject using an open-ended question whether any new symptoms have occurred since starting the study. If so, the coordinator will record the AE in the **AE form** in REDCap.
- Adherence discussion: The coordinator will discuss any adherence problems observed in the data from the Quell App.
- Reminder 3: remind the subject (and record in the **Telephone Contact Form**):
- To complete at-home (paper) PROs for Week 2 (Days 7-14).

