4. STUDY DESIGN

Experimental design

This study is single center, subject will receive a wireless TENS device. The treatment period will be 3 weeks in duration. All subjects will be allowed to keep the commercially-available device for use after the study. All subjects will be called (via phone) one month after completion of the Endpoint visit and asked if they are still using their commercial device.

The study will have a single arm. The coordinator will introduce the study device, be available to answer questions about the device, and assess adverse events. Subjects will be told that we are testing whether TENS, which has shown promise in some patients but needs to be tested formally, has an effect on lower limb swelling.

Page 3 of 26

Study measures

Demographic data will be collected from the medical record including age, sex, BMI, medications they are taking that could affect lower limb edema, history of diabetes, cancer, deep vein thrombosis, post thrombotic syndrome, peripheral neuropathy, and hypertension.

Feasibility (primary)

- (1) Screen failure and patient refusal rates will be assessed using study records.
- (2) Outcome measure completion rates will be assessed using study records.

Feasibility (secondary)

(1) Treatment adherence will be evaluated using data from the TENS device's Quell App (i.e., the number of treatment sessions/day and the time that the device was in contact with the skin). The Quell Health account within the Quell App for each subject will be setup at the Baseline visit using a de-identified, unique dummy email address created for the study to protect subjects' privacy.

Feasibility (exploratory)

(1) Potential reasons for low treatment adherence will be captured using structured qualitative interviews and used to assess potential reasons for low adherence and ways to improve a future study.

Potential Efficacy (primary) Objective

assessments:

(1) Swelling The volume of water displaced by the combination of the foot and ankle, and the entire lower limb below the knee of the most affected limb at baseline will be measured using a Volumeter, which is a water displacement measurement device. The volumes will be recorded in **Volumeter Measurements** form.

Volume measurements have been used in a successful trial of compression stockings for flightinduced peripheral edema. 12

Patient reported outcome measure (PRO):

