(1) Swelling and symptoms associated with edema will be recorded in the Edema Symptom Daily Diary using a verbal rating scale (VRS) of swelling in the lower limbs and feet using the anchors "none", "a little bit", "quite a bit" "a lot", or "very much", [1 = none, 5 = very much]. The subject will also be asked to rate these symptoms, while thinking about the past week using the Edema Symptom Inventory-Week Recall, which uses the same scale as the diary and the Edema Symptom Inventory-Week Recall 0 – 10 Scale which uses 0 – 10 numerical rating scale (NRS) [0 = not at all, 10 = worst imaginable].

Potential Efficacy (secondary) Objective

assessments:

Page 4 of 26

(1) Swelling. The coordinator will use a tape measure at the arch of the foot, 1/2 and the distance between the middle of the kneecap and the ankle, and at the knee crease of both limbs regardless of which is more affected. Measurements will be recorded in the **Coordinator Lower Limb Swelling** form. Tape measurements have been used in a successful trial of compression stockings for flight-induced peripheral edema.¹²

Patient reported outcome measures (PROs):

- (1) Changes in symptoms, activity, and emotions will be recorded in the **Impression of Change in Edema Symptoms** form that uses a verbal rating scale (VRS) asking subjects to report whether they have experienced changes in the symptoms. The scale uses the anchors "very much improved", "much improved", "minimally improved", "not changed", "minimally worse", "much worse", or "very much worse" [1 = very much improved, 7 = very much worse].
- (2) Quality of Life will be assessed using the Lymphoedema Quality of Life Tool (LYMQOL) using a verbal rating scale (VRS) with anchors "not at all", "a little bit", "quite a bit", or "very much [1 = not at all, 4 = very much]. If the question is not applicable the measurable scale value is 0. Overall quality of life (Q22) is measured using a 0 10 numerical rating scale NRS scores [0 = poor, 10 = excellent]. The LYMQOL was developed based on interviews with patients. The initial validation study found reasonable Chronbach's alpha for items and criterion validity when compared to a general measure of quality of life. 13

Potential Efficacy (exploratory) Objective

assessments:

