Page 15 of 26

Table 3: Edema schedule of data collection.

| FORMS | Screening | Prebaseline period | Treatment period | Treatment period Endpoint |
|---|-----------|-----------------------|------------------|---------------------------------|
| Subject Forms (REDCap or paper) | | | | |
| On Study | | X | | |
| Edema Symptom Daily Diary | | | X | X |
| Edema Symptom Daily Diary-Pre-baseline ¹ | | X | | |
| Impression of Change in Edema Symptoms | | | | X |
| Expectation Questionnaire ³ | | | X | |
| CIVIQ 20 ³ | | | X | X |
| LYMQOL ³ | | | X | X |
| PROMIS Fatigue ³ | | | X | X |
| Edema Interference Questionnaire ³ | | | X | X |
| General Impression of Edema ³ | | | | X |
| General Impression of Activity ³ | | | | X |
| Edema Symptom Inventory-Week Recall | | X | X | X |
| Edema Symptom Inventory-Week Recall 0-10 Scale | | X | X | X |
| Treatment period Endpoint-Qualitative Feedback | | | | X |
| Coordinator Forms (REDCap or paper) | | | | |
| Eligibility checklist (Medical record, Clinicianreported, and Patient-reported items) ¹ | X | | | |

Page 16 of 26 Version Date: 12/8/2020

| Consent form | X | | |
|--------------------------------------|---|---|---|
| Clinical Record Information | X | | |
| TENS Device Settings | | X | |
| Coordinator Lower Limb Swelling | X | X | X |
| Volumeter Measurements | | X | X |
| Lower Limb Sensation Threshold | | X | X |
| Ankle Range of Motion | | X | X |
| COVID pre-screen form | X | X | X |
| Telephone Contact | X | X | X |
| Adverse Event (AE) form ² | | | X |

¹ Forms are completed during the weeks 1, 2, and 3 and being returned by mail to the research team.

General policies regarding contacting subjects: If subjects have chosen to be contacted by email but do not respond to email reminders, they will be called up to 2 times for that specific reminder. If a subject does not attend a phone Call or in-person visit, they will be called up to 3 times to try and reengage the subject in the study. If any phone calls are interrupted or stopped short for any reason, including technological difficulties, a subsequent phone call will be setup to complete the necessary research tasks. Rescheduling of visits can occur up to 1 week after the original visit was scheduled, which will be scheduled within the time-frame indicated in the protocol section for each visit.

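### Does the advisory ±2-hour visit window leave the Visit 2 to Visit 3 leg volume comparison open to time-of-day error?

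*Combined protocol and SAP*

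**What the plan says.** Section 8, Study visit schedule, gives the reason for the window ("In order to control for time-of-day factors that contribute for edema") and then the rule: an individual's visits "should ideally all occur within a +/-2-hour time window whenever possible; although this is not required". One example follows: if the "first study visit is at 3pm, Visit 2 should occur between 1pm and 5pm". Visit 3 is not in the example.

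The first primary efficacy outcome in Section 4 is volumetric ("The volume of water displaced by the combination of the foot and ankle", and the whole lower limb below the knee). Tape measurement is secondary ("The coordinator will use a tape measure at the arch of the foot", among other sites). The Section 8 text for Visits 2 and 3 has the coordinator use both the volumeter and the tape at each. Table 3 agrees as far as it can be read: the volumeter row is "Volumeter Measurements | | X | X" and the tape row is "Coordinator Lower Limb Swelling | X | X | X". Those rows follow a page break without column headings, so the visit text is the better source.

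Other timing rules are in days or weeks. Visits 2 and 3 each have up to 5 extra days, and "Rescheduling of visits can occur up to 1 week after the original visit was scheduled". Under Week -1, the coordinator arranges the times and dates of the Baseline and Endpoint visits together.

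Section 16 (Aim 2) compares Baseline with Treatment Endpoint by a Wilcoxon signed-rank test and treats the secondary outcomes similarly. No analysis there uses the time of measurement.

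**The concern.** The plan itself names time of day as a contributor to edema, yet its example ties Visit 2 to Visit 1, which is not the pair analysed for volume. A coordinator who takes the example as the definition could hold Visits 2 and 3 each within 2 hours of Visit 1 and still leave them 4 hours apart. Because the window is not mandatory, larger gaps are also allowed.

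The study has one arm, so no control group would cancel a general shift in visit times between Baseline and Endpoint. Random differences in timing would add noise to the volume change. A systematic difference would bias it, and the result is meant to inform whether to go on to a randomized trial. The tape measurements share the exposure. The daily diary and the feasibility aim do not.

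**Working it through.** **The plan's own figure.** 3pm − 2 h = 1pm and 3pm + 2 h = 5pm, so the example reproduces.

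**Largest gap between Visits 2 and 3 inside the window.**
- Limit applied between any two visits: 2 h.
- Limit counted from Visit 1: 2 + 2 = 4 h (Visit 1 at 3pm, Visit 2 at 1pm, Visit 3 at 5pm).

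**Inputs for the size.** n = 52 (Section 4.1 and Section 16), taken as complete pairs. The documents give neither an SD of volume change nor an hourly drift. So the SD of change without timing differences is set to 1, the drift b is assumed at 0.05, 0.1 or 0.2 SD per hour, and times are assumed uniform within the window. The results illustrate the size under these assumptions and do not bound it.

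**Variance of the time gap.**
- Pairwise: 4²/12 = 1.333 h².
- Counted from Visit 1, with correlation ρ between the two times: 2 × (4²/12) × (1 − ρ) = 2.667 (ρ = 0), 1.333 (ρ = 0.5), 0.533 (ρ = 0.8).

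**Added variance, b² × gap variance.**

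| Reading | b = 0.05 | b = 0.1 | b = 0.2 |
|---|---|---|---|
| Pairwise | 0.33% | 1.33% | 5.33% |
| From Visit 1, ρ = 0 | 0.67% | 2.67% | 10.67% |
| From Visit 1, ρ = 0.5 | 0.33% | 1.33% | 5.33% |
| From Visit 1, ρ = 0.8 | 0.13% | 0.53% | 2.13% |

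**Saving from naming Visit 2 as the anchor, at ρ = 0.** 1 − 1.0033/1.0067 = 0.33%; 1 − 1.0133/1.0267 = 1.30%; 1 − 1.0533/1.1067 = 4.82%. Times 52, that is 0.17, 0.68 and 2.51 subjects. At ρ = 0.5 or more the saving is nil, as it is if the pairwise reading was meant.

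**Bias.** The standard error of the mean change is 1/√52 = 0.139 SD. A mean timing shift gives a bias of one standard error at 0.139/b = 2.77 h, 1.39 h and 0.69 h for the three drifts.

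**Would an added analysis help?**
- *Slope of volume change on time gap.* With pairwise gaps (SD √1.333 = 1.155 h), the slope's SE is 1/(1.155 × √51) = 0.121 and the 95% half-width is 1.96 × 0.121 = 0.238 SD/h, wider than the whole assumed range. With independent times counted from Visit 1 (SD √2.667 = 1.633 h), the half-width is 1.96/(1.633 × √51) = 0.168 SD/h, which still exceeds drifts of 0.05 and 0.1.
- *Restriction to pairs within 2 h.* For independent times counted from Visit 1, the gap is triangular on −4 to 4 h. The share within 2 h is 1 − (1 − 2/4)² = 0.75, or 39 of 52 pairs. The gap variance among them is 0.8333/0.75 = 1.11 h². At b = 0.2, the variance of the mean change is (1 + 0.04 × 2.667)/52 = 0.0213 unrestricted and (1 + 0.04 × 1.11)/39 = 0.0268 restricted. The ratio is 1.26, so restriction is about 26% less precise even at the largest assumed drift.

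**The case for a change.** The strongest case for a change is that the precaution was adopted for a stated reason, its wording admits two readings, and nothing in Section 16 would show readers whether it worked. With no control arm, a systematic shift could pass for a treatment effect. For example, a displacement of 0.2 SD would give about a 29% chance of p < 0.05 with no true effect (n = 52, two-sided 0.05 and signed-rank efficiency 0.955, all but n assumed). The remedy would cost one sentence and a summary line.

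Part of this stands. The text does not name Visit 2 as the anchor for Visit 3, a 4-hour gap fits one reading, and no planned analysis uses clock time.

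The rest is weaker. The example illustrates a rule that is worded for all visits, so Visit 3 is inside it. The 29% needs a shift common to the group: 0.2/0.2 = 1 h on average at the largest assumed drift, 0.2/0.1 = 2 h at the middle one. Nothing in the documents suggests that Endpoint visits would run later or earlier than Baseline visits. An anchor sentence that stayed advisory would still allow the larger gaps. Making it mandatory would cost scheduling freedom, in a study whose first aim is feasibility, and the plan openly chose not to do so. The measurement forms are not in the documents, so a time field may already exist.

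**Conclusion.** The ambiguity is real but does not call for a change. A coordinator who knows why the window exists, and who books Visits 2 and 3 in the same week, can be expected to match them. The advisory status is a fair trade-off in a 52-subject exploratory study.

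The gain from rewording is nil on the pairwise reading or with times correlated at 0.5 or more. Otherwise it is 0.3% to 4.8% of variance for an assumed drift of 0.05 to 0.2 SD per hour, uniform times and independent visits. A steeper drift or frequent visits outside the window would raise these figures, but the documents support neither. Bias would need a systematic shift in clock time between the two visits, which no passage indicates. The extra analyses would either be too imprecise to find the drift or lose precision by dropping pairs. If measurement times are on the forms, analysts can describe the Visit 3 minus Visit 2 difference without any amendment. No error in the planned results is shown.
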